1.3 DETERMINATION OF SAMPLE SIZE

Sample size for the TDR12857 study was based upon empirical considerations. LTS13769 is the extension study of TDR12857; therefore, the number of patients in LTS13769 was determined by the subgroup of TDR12857 patients who consented to continue in the extension study. Thus, no formal sample size calculations have been performed for the TDR12857 or the LTS13769 study.

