2.1.6 Pharmacodynamic endpoints

Skeletal muscle MRI

Skeletal muscle magnetic resonance imaging (MRI), aiming to assess disease severity and detect treatment effects, will be performed prior to the muscle needle or open biopsy procedure, using both qualitative (T1) and quantitative (T2, Dixon) modalities. The images will be read and analyzed centrally.

T1 weighted axial data will be analyzed using the Mercuri scale, which determines degree of intact muscle and fatty replacement, providing a qualitative measure of overall disease severity. The Mercuri scale (grade 1-4) is as follows: (1) normal appearance, (2) mild involvement, (3) moderate involvement, and (4) severe involvement.

Volumetry: trophicity changes will be evaluated for 5 muscle groups, including the upper leg muscles (quadriceps, hamstring) and the lower leg muscles (triceps, extensors, fibularis). The measured area of each muscle group, cross-sectional area (CSA), will be provided (in mm²).

T2: multi-slice multi-spin echo (MSME) and B1 mapping will provide a quantitative measure of disease activity (edema, inflammation) within muscles, measured in milliseconds (ms) (abnormal value defined as >39 ms).

Three-point Dixon imaging will provide quantification of fat content in muscles (fat fraction [FF], described in percentages). The fat fraction will also be combined with the CSA measurements trophicity) to provide an Index of Real Muscle Mass (IRMM) in mm² (IRMM = CSA * [1 – FF]).

Skeletal muscle needle or open biopsy

Skeletal muscle needle or open biopsy will be performed on the lower extremity (quadriceps) muscle to assess glycogen content. The MRI appearance of the muscle will be used to determine the level (axial slice position) that the biopsy procedure should target (avoiding fatty replaced tissue). Glycogen content will be measured by histomorphometric analysis or severity grading to determine how effectively avalglucosidase alfa is able to remove glycogen from muscle.

Urinary Hex4 level

Assessment of urinary Hex4 concentrations will be assessed from fasted urine samples.

Exploratory urine and plasma biomarkers

Fasted plasma and urine samples will be collected prior to IMP infusion for the assessment of exploratory biomarkers. The analysis of biomarkers will be planned and reported separately.

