2.4.5 Analyses of safety data

The summary of safety results will be presented by dose and patient group. Corresponding listings will also be presented.

General common rules

All safety analyses will be performed on the safety population as defined in [Section 2.3.2](#), unless otherwise specified, using the following common rules:

- The baseline value is defined as the last value prior to the first dose of GZ402666 in the TDR12857 study
- The re-baseline values is defined as the last non-missing assessment before patients switch to 20 mg/kg dose for LTS-switch patients.
- The potentially clinically significant abnormality (PCSA) values are defined as abnormal values considered medically important by the Sponsor according to predefined criteria/thresholds based on literature review and defined by the Sponsor for clinical laboratory tests, vital signs, and ECG (PCSA version dated May 2014 [Appendix A])
- PCSA criteria will determine which patients had at least 1 PCSA during the treatment-emergent adverse event period, taking into account all evaluations performed during the treatment-emergent adverse event period, including nonscheduled or repeated evaluations. The number of all such patients will be the numerator for the on-treatment PCSA percentage
- The treatment-emergent PCSA denominator by group for a given parameter will be based on the number of patients assessed for that given parameter in the treatment-emergent adverse event period by dose and patient group on the safety population.
- For quantitative safety parameters based on central laboratory/reading measurements, descriptive statistics will be used to summarize results and change from baseline values by visit and treatment group.
- The analysis of the safety variables will be essentially descriptive and no systematic testing is planned. Relative risks between groups and their 95% confidence intervals may be provided, if relevant.

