- Incidence of neutralizing antibodies (inhibition of enzyme activity and inhibition of enzyme uptake) will be reported for both treatment naïve and switch patients
- Onset time of neutralizing ADA will be analyzed descriptively using summary statistics minimum, Q1, median, Q3 and maximum.
- Duration of neutralizing ADA will be analyzed descriptively using summary statistics minimum, Q1, median, Q3 and maximum. It will only be calculated for the patients with at least two ADA positive samples.

The following listings will be provided:

- Anti-avalglucosidase alfa alfa antibody titer values, neutralizing antibody, circulating immune complex, anti-avalglucosidase alfa IgE antibody, serum tryptase activity, complement activation, and skin testing performed
- Listings of anti-avalglucosidase alfa ADA and inhibitory antibodies
- Listings of anti-alglucosidase alfa ADA and inhibitory antibodies

Association of ADA with PK

The following analysis will be considered for switched patients: 1. Within Subject level AUC change from baseline to the last injection will be plotted by peak titer category. Gender will be separated by different color. 2. Between subject comparison of ADA-positive vs. ADA negative. Plot of AUC at baseline compared to timepoints where full PK assessment is available. Patients will be evaluated by titer categories based on titer category at the time of PK assessment. Patients will be separated based on treatment groups. 3. Summary table to include AUC and % change from Day 1 at each scheduled visit by peak titer categories. 4. Data will be assessed for switch patients as appropriate.

Association of ADA and PD marker

Hex-4 is a clinically relevant PD marker that is related to the drug's mechanism of action. Summary table of number (%) of patients with elevated urinary hex-4 by titer value at the specified visit (eg, peak titer categories) over time will be provided.

Evaluation of ADA on Relevant Safety Parameters

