To evaluate the effect of ADA and NAb on AEs, the number and percentage of patients experiencing any TEAEs, any treatment-emergent SAEs, or any IARs, hypersensitivity (narrow SMQ), and Anaphylactic reaction (narrow SMQ) will be presented by the following sub-categories: 1. ADA status (ever positive, always negative) 2. ADA peak titer category (always negative, peak titer 100-800, 1600-6400, $\geq 12,800$) 3. ADA response type (always negative, transient response (if occur), and persistent responses subcategories: low response, intermediate response, high ADA response and tolerized at defined timepoints. 4. Correlation of frequency of IAR and ADA peak titer. 5. Neutralizing antibody status (always negative, ever positive).

Association of ADA with selected efficacy

Correlation analysis will be performed between immunogenicity (ADA titers, response categories and neutralizing ADA) and FVC, 6MWT, (raw and percent predicted), MIP, MEP.

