Urine Hex4 levels will be summarized using descriptive statistics at each scheduled study visit. Observed measurements, as well as change from baseline, will be summarized. If a linear trend in the change of urine Hex4 levels is observed, a longitudinal model may be employed to model change from baseline over time. In addition, 95% CIs of changes will be presented. Due to the small number of patients, nonlinear relationship will not be formally characterized.

PK and urine Hex4

To explore the relationship between PK endpoints and urine Hex4 levels, correlational statistics (Spearman or Pearson) at select visits where PK and urine Hex4 are assessed will be used. In addition, scatter plots and linear regression analysis may be used to describe the relationship between PK endpoints and urine Hex4 levels as appropriate.

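### SAP 2.4.5.6 examines antibodies against urinary Hex4 only as a count of elevated patients by titer, with no cut-off, no patient baseline and an unclear titer variable, where a correlation would keep the information

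*SAP*

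**What the plan says.** SAP 2.4.5.6, under the association of ADA with the PD marker, presents Hex4 as clinically relevant and tied to the drug's mechanism. It then plans one output: "Summary table of number (%) of patients with elevated urinary hex-4 by titer value at the specified visit". The parenthesis that follows reads "eg, peak titer categories) over time will be provided". So the titer grouping is only an example, and the table is repeated over visits.

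Other parts of the SAP bear on this:

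- **Scale of Hex4 (2.1.6):** "Assessment of urinary Hex4 concentrations will be assessed from fasted urine samples". Section 2.4.7 summarises observed Hex4 and its change from baseline by visit, with 95% CIs, but not by ADA.
- **ADA against efficacy (2.4.5.6):** "Correlation analysis will be performed between immunogenicity (ADA titers, response categories and neutralizing ADA) and FVC", and likewise for 6MWT, MIP and MEP. Hex4 is not on that list.
- **PK against Hex4 (2.4.7):** Spearman or Pearson correlation at visits where both are measured, with optional scatter plots and regression.
- **Study size (1.3 and 2.4.7):** "Thus, no formal sample size calculations have been performed for the TDR12857 or the LTS13769 study", and, in the Hex4 text, "Due to the small number of patients, nonlinear relationship will not be formally characterized".
- **Status of the section (2.4.5):** "The analysis of the safety variables will be essentially descriptive and no systematic testing is planned".

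**The concern.** The clinical question is whether antibodies blunt the pharmacodynamic response. The planned table answers it weakly, for three reasons that need no power calculation.

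1. **Elevated is undefined.** Without a stated limit, the cut can be chosen after the data are seen, and two analysts could produce different tables.
2. **The patient's own baseline is not used.** Let B be baseline Hex4, Y the on-treatment value and L the unstated limit. The table records only whether Y > L. A patient with B far above L can have a large fall and still count as elevated. A patient with B well below L can rise substantially and never be counted. Neither patient's response to treatment is visible.
3. **The titer variable is ambiguous.** Titer at the visit and peak titer are different quantities. A peak can occur after the Hex4 sample, so grouping an early Hex4 value by peak titer classifies it by something that had not yet happened.

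With few patients, a yes/no count by titer is also sparse. A moderate association could go unseen in a marker the SAP itself regards as informative.

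**Working it through.** **Step 1. Is there another ADA-Hex4 analysis?** None was found. Protocol 11.6.2 plots ADA and neutralizing titers against clearance. Protocol 11.7 relates Hex4 to PK, and the PD endpoints to one another and to efficacy. SAP 2.4.7 relates Hex4 to PK. Only the table in SAP 2.4.5.6 joins ADA and Hex4.

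**Step 2. Is there a cut-off?** None was found. SAP 2.1.6 states a limit for another PD measure (MRI T2, abnormal above 39 ms) but none for Hex4, and Hex4 is not among the Appendix A criteria.

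**Step 3. Which titer?** The only titer classes listed are for the safety tables: "ADA peak titer category (always negative, peak titer 100-800, 1600-6400", and 12,800 or more. For ADA and PK, the same section uses peak titer category in some items and category at the time of the PK assessment in another. The Hex4 sentence combines the two.

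**Step 4. Information lost by the Hex4 cut alone.** The documents give no n, correlation or share elevated, so there is no figure to reproduce. Assume bivariate normal log titer and log Hex4. Cutting Hex4 so that a share p is elevated multiplies the correlation by φ(c)/√(p(1−p)), where c is the normal quantile at 1−p.

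- p = 20%: 0.280/0.400 = 0.70; squared, 0.49.
- p = 50%: 0.399/0.500 = 0.80; squared, 0.64.

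The squared factor approximates the effective share of the sample that remains: about half to two thirds.

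**Step 5. Illustrative power if a test were run** (two-sided 5%). Formula: Φ(√(n−3)·atanh(r) − 1.96). With n = 20 and r = 0.5:

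- Measured Hex4: 4.123 × 0.549 − 1.96 = 0.305, so power is 62%.
- Hex4 cut at 20% elevated (r becomes 0.35): 4.123 × 0.365 − 1.96 = −0.453, so power is 32.5%.

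Simulation, 1,500 runs per row, compares Spearman on measured Hex4 with a linear trend test of elevated yes/no over four titer classes. Set A has 25% titer-negative, titer in steps, and classes cut at 25/60/85%. Set B has continuous titer with classes cut at quartiles.

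| Set | n | r | Elevated | Spearman | Trend | Loss (points) |
|---|---|---|---|---|---|---|
| A | 16 | 0.5 | 20% | 44% | 24% | 20 |
| A | 20 | 0.5 | 20% | 54% | 30% | 24 |
| A | 24 | 0.5 | 20% | 63% | 36% | 27 |
| B | 20 | 0.5 | 20% | 58.3% | 31.5% | 26.8 |
| B | 20 | 0.5 | 50% | 56.6% | 41.6% | 15.0 |
| B | 20 | 0.3 | 20% | 20.7% | 12.5% | 8.1 |
| B | 15 | 0.7 | 20% | 79.8% | 39.4% | 40.4 |
| B | 50 | 0.7 | 50% | 99.9% | 98.9% | about 1 |

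The direction is the same in every row. The size depends on the assumed inputs.

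**Step 6. Where can the two be paired?** Appendix B Table 5 has 20 post-baseline Hex4 visits. Table 3 has no ADA visit at Weeks 3, 7, 11, 15, 19 or 23. Both tables list Weeks 25, 52, 104, 156, 208, 260 and 312. The windows differ: at Week 52, Hex4 runs from the first day of LTS13769 to day 548, while ADA runs from day 351 to day 411. Matching on visit label alone could pair samples 548 − 351 = 197 days apart.

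**The case against.** The strongest reply is that this is a descriptive table in a section where no systematic testing is planned. A reader might infer that the plan forfeits a definite amount of power. The documents do not support that: the trend test in the working is not in the SAP, and n, correlation and share elevated are all assumed. The loss was 8 to 50 points over one grid (n 16-24, r 0.4-0.6, 10-40% elevated) and about 1 to 40 over another (n 10-50, r 0.3-0.7, 20% or 50% elevated). This reply stands. What can be defended is loss of information.

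Three further readings go too far:

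- **That titer is fixed into a few classes.** The SAP gives peak categories only as an example. The Hex4 cut remains under any titer grouping.
- **That Hex4 is reduced to yes/no throughout.** Section 2.4.7 reports it on the measured scale with change from baseline, but not against ADA. If the over-time display includes baseline, it shows the baseline share elevated by group, but still does not link a patient's value to that patient's baseline.
- **That a sparse table would be reported as no antibody effect.** That predicts misuse and is not in the plan.

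SAP 1.6 says the immunogenicity analysis was aligned with an integrated immunogenicity plan, which is not available here. That plan may define elevated. If so, this SAP should repeat or cite the limit.

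Finally, a continuous analysis will also be imprecise. With n = 20 and an observed correlation of 0.5, the approximate 95% interval is tanh(0.549 ± 1.96/√17), or 0.07 to 0.77. That argues for reporting an interval, not for cutting the data first.

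**Conclusion.** The point holds as a matter of information and definition. The only planned ADA-Hex4 output turns a concentration into yes/no at an unstated limit, leaves out each patient's baseline and does not settle which titer is used. The SAP already uses correlation for the neighbouring ADA-efficacy and PK-Hex4 questions.

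Under bivariate normality, the Hex4 cut alone leaves roughly half (20% elevated) to two thirds (50% elevated) of the effective sample. The illustrative power comparison at n = 20, r = 0.5 and 20% elevated is about 54-58% against 30-32%. These figures rest on assumed inputs and describe no test in the plan.

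This is a worthwhile, low-cost improvement to an exploratory analysis. It does not affect the primary safety assessment.

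**What to change.** Keep the table as a display. In SAP 2.4.5.6:

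1. State the limit for elevated Hex4, with units and source, and state whether titer is that of the visit or the peak to date.
2. Add an exploratory Spearman correlation of log2 ADA titer with Hex4 percent change from the TDR12857 baseline, with a 95% CI and a scatter plot coded by patient and dose group. Rank negatives lowest: SAP 2.5.3 sets them to 0, which has no logarithm. The log does not alter Spearman and serves the plot.
3. Limit this to a short prespecified list of visits where both are scheduled, for example Weeks 25, 52, 104 and yearly thereafter, and pair samples by date with a stated maximum gap. Using every Hex4 visit would include visits with no ADA sample and multiply the correlations.
4. If n allows, add a supportive mixed model of log Hex4 on same-visit log2 titer. Adjust for baseline log Hex4, patient group (naive or previously treated) and dose, include a random patient effect, and state the value given to negatives.

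**Cost:** SAP wording and one or two exploratory outputs; Hex4 and titers are already collected. There will be several unadjusted correlations. At the seven visits Weeks 25 to 312, with no true association, 7 × 0.05 = 0.35 intervals would be expected to exclude zero. They should be read as estimates with intervals, not as tests.

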10.4.2 General guidelines for reporting adverse events

- All AEs, regardless of seriousness or relationship to IMP, spanning from the signature of the informed consent form until the end of the study as defined by the protocol for that patient, are to be recorded on the corresponding screen(s) of the eCRF.
- When a safety event is categorized as a primary outcome, the event will be reported as an AE but will be waived from reporting to health authorities providing an agreement has been reached with them.
- Whenever possible, diagnosis or single syndrome should be reported instead of symptoms. The Investigator should specify the date of onset, intensity, action taken with respect to IMP, corrective treatment/therapy given, additional investigations performed, outcome, and his/her opinion as to whether there is a reasonable possibility that the AE was caused by the IMP.
 - There is one exception to this rule. In instances where a patient experiences an IAR (refer to [Section 8.8.2](#)), allergic, or anaphylactic reaction, either during infusion or post observation period, each of the individual signs and/or symptoms comprising the reaction should be captured as individual AE terms.
- The Investigator should take appropriate measures to follow all AEs until clinical recovery is complete and laboratory results have returned to normal, or until progression has been stabilized, or until death, in order to ensure the safety of the patients. This may imply that observations will continue beyond the last planned visit per protocol, and that additional investigations may be requested by the monitoring team up to as noticed by the Sponsor.
- When treatment is prematurely discontinued, the patient's observations will continue until the end of the study as defined by the protocol for that patient.
- Laboratory, vital signs, or ECG abnormalities are to be recorded as AEs only if:
 - Symptomatic and/or,
 - Requiring either corrective treatment or consultation, and/or,
 - Leading to IMP discontinuation or modification of dosing, and/or,
 - Fulfilling a seriousness criterion, and/or,
 - Defined as an AESI.

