2.1.4.1 Adverse events variables

Adverse event observation period

- Pretreatment adverse events are adverse events that developed or worsened or became serious during the screening epoch
- Treatment-emergent adverse events are adverse events that developed or worsened or became serious during the treatment-emergent adverse event period
- Posttreatment adverse events are adverse events that developed or worsened or became serious during the posttreatment period

All adverse events (including serious adverse events (SAE) and adverse events of special interest [AESI]) will be coded to a lowest level term (LLT), preferred term (PT), high-level term (HLT), high-level group term (HLGT), and associated primary system organ class (SOC) using the version of Medical Dictionary for Regulatory Activities (MedDRA) in effect at Sanofi at the time of database lock.

Recording of the occurrence of adverse events (including SAEs and AESIs) will be from the time of signed informed consent of the TDR12857 study until the end of the patient's participation in the TDR12857 or LTS13769 study.

Adverse event of special interest (AESI)

An adverse event of special interest (AESI) is an AE (serious or nonserious) of scientific and medical concern specific to the Sponsor's product or program, for which ongoing monitoring and immediate notification by the Investigator to the Sponsor is required. Such events may require further investigation in order to characterize and understand them.

AESIs will include the following:

Infusion-associated reactions (IAR):

Two definitions will be used in the analysis of IARs:

- Protocol-defined IARs: As defined in the protocol, IARs are defined as AEs that occur during either the infusion or the post-infusion observation period (ie, up to 2 hours or longer following the infusion as per the Investigator's discretion) which are deemed to be related or possibly related to the IMP. At the discretion of the Investigator, AEs occurring after the completion of the post-infusion observation period that are assessed as related may also be considered IARs by the Investigator.
- Algorithm-defined IARs: an alternative definition of IAR is defined as any treatment-emergent AEs meeting one of the following criteria:
 - a) Event occurs from the start of infusion to the end of infusion plus 24 hours window, and considered related to study drug;

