Analysis of all treatment-emergent serious adverse event(s)

- All treatment-emergent serious adverse events by primary SOC and PT, showing the number (%) of patients with at least 1 serious treatment-emergent adverse event and number of events, sorted by the internationally agreed SOC order and by decreasing incidence of PTs within each SOC.
 - Additional summaries of before- and after-rebaseline periods will be presented for the LTS-switch group
- All treatment-emergent serious adverse events regardless of relationship and related to IMP, by primary SOC and PT, showing the number (%) of patients with at least 1 treatment-emergent serious adverse event and number of events, sorted by the internationally agreed SOC order. The PT levels will be presented in alphabetical order.
 - Additional summaries of before- and after-rebaseline periods will be presented for the LTS-switch group
- All treatment-emergent serious adverse events by maximal severity, presented by primary SOC and PT, showing the number (%) of patients with at least 1 treatment-emergent adverse event and number of events by severity (ie, mild, moderate, or severe), sorted by the internationally agreed SOC order and by decreasing incidence of PTs within each SOC.
 - Additional summaries of before- and after-rebaseline periods will be presented for the LTS-switch group

Analysis of all treatment-emergent adverse event(s) leading to treatment discontinuation

- All treatment-emergent adverse events leading to treatment discontinuation, by primary SOC and PT, showing the number (%) of patients and number of events sorted by the internationally agreed SOC order. The PT level will be presented in alphabetical order

Analysis of standardized MedDRA query

A comprehensive programming search of AEs which meet the Standardized MedDRA Query (SMQ) criteria for hypersensitivity and anaphylactic reaction will be used to identify adverse events that potentially are associated with symptoms of anaphylactic and hypersensitivity reaction.

Results of this search will be provided in a by patient listing by group. The most recent version of MedDRA SMQ will be used at the time of analysis. A medical review of these cases will be performed.

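### The anaphylaxis row in the ADA-by-safety table uses only the narrow SMQ, while the protocol has sites record anaphylactic reactions as separate symptoms, so the row may undercount

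*SAP*

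**What the plan says.** Protocol 10.4.2 gives the general recording rule: "Whenever possible, diagnosis or single syndrome should be reported instead of symptoms". It then adds "There is one exception to this rule", which applies to an IAR, "allergic, or anaphylactic reaction, either during infusion or post observation period, each of the individual signs and/or symptoms comprising the reaction should be captured" as separate AE terms.

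SAP 2.4.1 and the sections around it define the groups; SAP 2.1.4.1 codes each AE to MedDRA levels, including the preferred term. Under the part of SAP 2.4.5.6 that evaluates ADA against safety parameters, patients with any TEAE, any treatment-emergent SAE, any IAR, "hypersensitivity (narrow SMQ), and Anaphylactic reaction (narrow SMQ) will be presented by the following sub-categories". The sub-categories are ADA status, peak titer band, ADA response type and neutralizing antibody status. A correlation of IAR frequency with peak titer is listed alongside.

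SAP 2.4.5.1 separately plans an SMQ search for hypersensitivity and anaphylactic reaction, to "identify adverse events that potentially are associated with symptoms of anaphylactic and hypersensitivity reaction". The results go into a by-patient listing by group, and "A medical review of these cases will be performed". The scope of that search (narrow, broad or a combination of terms) is not stated.

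**The concern.** The recording rule and the search rule pull in opposite directions. The protocol asks sites to break an anaphylactic reaction into its components. The table that is meant to relate antibodies to anaphylaxis then looks for it with the scope that depends most on the diagnosis being named. A reaction entered as, say, urticaria, bronchospasm and hypotension could leave no trace in the anaphylaxis row.

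Safety is the primary endpoint and includes immunogenicity (Protocol 9.1), and Protocol 4.2.2.1 treats immune reactions to the enzyme as critical to its safety. An anaphylaxis row that is empty or nearly so in every ADA, titer and neutralizing antibody category could be read as showing no antibody effect when it partly reflects how the reactions were recorded.

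**Working it through.** The plan gives no figure to reproduce: neither document states an anaphylaxis count or rate, or how often sites enter the diagnosis. The check is therefore to follow one reaction from the site to the table.

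1. **Recording (Protocol 10.4.2).** An anaphylactic reaction falls under the stated exception, so its signs and symptoms are entered one by one. The amendment 08 and 09 change tables list no change to this section, so the mismatch does not come from the SAP (signed March 2020) predating the current protocol.
2. **Coding (SAP 2.1.4.1).** Coding works on the entered term. A symptom codes to a symptom preferred term.
3. **Search (SAP 2.4.5.6).** The anaphylaxis row accepts narrow-scope terms only. No combination rule and no reviewed case definition is given for it.
4. **Possible repair elsewhere.** I looked for any output that gives anaphylaxis by antibody category in another way:
   - SAP 2.4.5.1 search and medical review: the output is a by-patient listing, with no instruction to carry reviewed cases into 2.4.5.6.
   - SAP 2.4.5.1 table of TEAEs by SMQ and PT: it follows the sentence on immune-mediated reactions and is not split by ADA, titer or neutralizing antibody.
   - IAR rows in 2.4.5.6: split by the right categories, but they mix anaphylaxis with every other related infusion reaction.
   - SAE and hypersensitivity rows: same limitation, and the hypersensitivity row is also narrow scope.
   - By-patient listings of AEs with ADA and IgE (2.4.5.1), and of titer, neutralizing antibody, IgE, tryptase, complement and skin testing (2.4.5.6): individual data, no comparison.

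   None supplies the missing cases to the anaphylaxis row.

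**Size, on an assumption.** Let p be the true proportion of patients with anaphylaxis in an ADA category, and s the share of those patients recorded by symptoms alone. If single symptoms lie outside the narrow scope, the row shows

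shown proportion = p × (1 − s)

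- s = 0 (diagnosis always also entered): p, no loss.
- s = 0.5: 0.5p, half lost.
- s = 1 (symptoms only, always): 0 in every category.

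With the same s in two categories, the difference shown is (p1 − p0) × (1 − s), so a true difference shrinks in proportion and disappears at s = 1. In counts, purely for illustration, 4 affected ADA-positive patients give 4 × (1 − 0) = 4, 4 × (1 − 0.5) = 2, 4 × (1 − 0.75) = 1 or 4 × (1 − 1) = 0 in the table.

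**The case against.** Several points on the other side have weight.

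- **The SMQ content is not in the documents.** Neither document lists the narrow terms or says that symptoms fall outside them. This stands as a declared assumption. It rests on the ordinary meaning of a narrow search and is the reason for saying that the row may undercount.
- **Loss is not certain.** A reader might infer that real reactions are bound to be missing, or that capture is zero. The documents do not support that. Protocol 10.4.2 asks for symptom terms but does not forbid entering the diagnosis as well, and Protocol 6.3.3.2 itself uses anaphylactic reaction as an example of an AE. The analysis also pools TDR12857 (SAP section 2), whose recording rule cannot be seen. Zero capture is only the end of the range.
- **The other search need not be wider.** A reader might also infer that the SAP 2.4.5.1 search already casts a broader net. It is described as comprehensive, but no scope is given, so this remains an inference.
- **There is real mitigation.** A related reaction during infusion or observation is an IAR by definition, and the algorithm definition in SAP 2.1.4.1 reaches to 24 hours after infusion. Such a patient would still be counted in the IAR row by ADA category, and IAR frequency is correlated with peak titer. The listings let a clinician link individual reactions to antibodies. With few patients and a descriptive analysis, single cases would probably be read individually. All of this limits the harm, but it leaves the anaphylaxis row itself unrepaired.
- **The narrow scope may be deliberate.** SAP 1.6 says the immunogenicity analysis was aligned with an integrated plan that is not available here. That is a good reason to keep the narrow row and add to it, not to replace it.

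**Conclusion.** The concern holds in a limited form. Followed as written, the recording rule and the narrow search can undercount anaphylaxis in the one row meant to show it by ADA status, titer, response type and neutralizing antibody status. No other planned output gives that breakdown.

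The undercount lies anywhere from none to all cases, and the documents do not narrow it. It rests on two assumptions: that narrow scope means terms naming the condition, and that some sites record symptoms without the diagnosis. No type I error or power is involved, since the safety analysis is descriptive. The risk is a falsely reassuring row. A reader might infer that the study would end up reporting no antibody effect on anaphylaxis; that goes too far, because the IAR rows, the titer correlation and the reviewed listing would all have to be ignored. This is worth correcting because the correction is cheap.

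**What to change.** In SAP 2.4.5.6, keep the narrow SMQ anaphylaxis row for consistency with the integrated plan. Next to it, add a row of anaphylaxis cases confirmed by the medical review already planned in SAP 2.4.5.1, shown by the same ADA status, peak titer, response type and neutralizing antibody categories.

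In SAP 2.4.5.1, state the scope of the search that feeds the review: it should cover symptom terms (broad or combination scope), grouped by infusion episode, and not the narrow scope alone. The SAP already works this way for severe cutaneous and immune-mediated reactions, where a search is followed by medical review against a definition (2.1.4.1) and a summary table (2.4.5.1).

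The cost is SAP wording and one derived flag for confirmed cases. No new data, visits or site procedures are needed. The broader search will bring in some false positives, which the medical review removes.
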